7.3 PLANNED ANALYSES

7.3.1 Primary analyses

The primary endpoint (measured from date of randomisation to end of observation period) is:

- Time to first MBE/CRNMBE

as determined by the IAC. It will be analysed using the stratified Cox proportional hazards regression model including factors for age (<80 or ≥80 years old) and treatment arm (110mg DE-DAT vs warfarin-TAT and 150mg DE-DAT vs warfarin-TAT). Models will be fitted for each comparison separately.

The primary analysis will be performed under the intention-to-treat framework on the full analysis set of patients (FAS) that includes all randomised patients (regardless of whether they have received treatment). Patients who discontinue study medication will be followed until the end of the trial. Patients who are lost to follow-up for vital status will be censored for the primary endpoint at the time of their last known vital status. All patients will be analysed according to the treatment arm to which they were randomised.

For the comparison of 110mg DE-DAT vs warfarin-TAT, patients of all ages and geographical regions will be included. For the comparison of 150mg DE-DAT vs warfarin-TAT, patients from the EU/ROW who are ≥80 years old will be excluded from the warfarin-TAT arm (as patients who are ≥80 years old from the EU/ROW are not randomised to 150mg DE-DAT).

The robustness of the primary analysis will be assessed by an on-treatment analysis. This on-treatment analysis will only count events that occur while a patient is taking study medication (including the REP of 6 days – see [Section 5.2.2.2](#)). It will also analyse patients by the actual treatment that was being taken while the event occurred.

Proprietary confidential information.

© 2016 Boehringer Ingelheim International GmbH or one or more of its affiliated companies. All rights reserved.

This document may not - in full or in part - be passed on, reproduced, published or otherwise used without prior written permission.

In addition, a sensitivity analysis will be performed that censors patients who switch from dabigatran to non-study warfarin or from study warfarin to non-study NOAC, at the time of the switch. The proportional hazards assumption will be investigated.

Kaplan-Meier curves will also be presented.

Subgroup analyses are planned and will be specified in the Trial Statistical Analysis Plan (TSAP).

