7.5 RANDOMISATION

Patients aged <80 years old will be randomly assigned to 110mg DE-DAT, 150mg DE-DAT or warfarin-TAT in a 1:1:1 ratio for the duration of the trial.

Proprietary confidential information.

© 2016 Boehringer Ingelheim International GmbH or one or more of its affiliated companies. All rights reserved.

This document may not - in full or in part - be passed on, reproduced, published or otherwise used without prior written permission.

Patients aged ≥ 80 years old will be randomly assigned depending on their geographical region:

- Patients aged ≥ 80 years old in the USA will be assigned to 110mg DE-DAT, 150mg DE-DAT or warfarin-TAT in a 1:1:1 ratio
- All other patients aged ≥ 80 years old (i.e. EU/ROW) will be assigned to 110mg DE-DAT or warfarin-TAT in a 1:1 ratio.

Patients will be randomised in permuted blocks, dynamically stratified by age (< 80 or ≥ 80 years old) and region (EU/ROW or USA) using an IRT. Dynamic stratification allocates blocks of randomisation numbers according to the strata of the first randomised patient within that block. For example, if the first patient randomised to the first block is < 80 years old and from the USA, other randomisation numbers within this block will only be allocated to patients < 80 years old from the USA (until there are no more randomisation numbers left to allocate within this block). BI will arrange for the packaging and labelling of study medication. The randomisation list will be generated using a validated system and a pseudo-random number generator so that the resulting treatment will be both reproducible and non-predictable. The block size will be documented in the CTR. Access to the codes will be controlled and documented.

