A2.23	Patients not willing or able to comply with the protocol requirements or considered unreliable by the Investigator concerning the requirements for follow-up during the study and/or compliance with study drug administration, who have a life expectancy less than the expected duration of the trial due to concomitant disease, or who have any condition which in the opinion of the Investigator, would not allow safe participation in the study (e.g. drug addiction, alcohol abuse).	Exclusion criterion 23 met	PPS

Table 6.2: 1 (continued) Important protocol violations

Category/ Code	Description	Example/Comment	Excluded from
B	Informed consent		
B1	Informed consent not given	Inclusion Criterion 4	All
B2	Informed consent given too late or the dates of the investigator's and patient's signatures do not match		None
B3	Informed consent withdrawn	Only applies from the date at which consent is withdrawn.	All
C	Trial medication and randomization		
C1	Incorrect trial medication taken	Medication kit assigned not matching treatment patient was randomised to (e.g. patient randomized to warfarin-TAT but received 110mg DE-DAT)	PPS
C2	Randomisation order not followed	e.g. forced randomization, mis-stratification	PPS
C3	Non-compliance	
Compliance <80% or >120% over the course of the study for dabigatran patients (determined on a visit-wise basis), or time in therapeutic target range for warfarin patients <45% (also on a visit-wise basis). See Section 7.3 for details on compliance calculations. Patients will be flagged if they exhibit non-compliance for two consecutive visits or more (for both dabigatran and warfarin patients).
 
Non-compliance caused by temporary interruption of treatment due to a procedure or a drop in CrCl to less than 30mL/min should not be classified as a protocol violation.
	PPS, but only from start of non-compliance onwards
C4	Trial medication taken at the wrong time	First dose of study drug not administered at the correct time (should be between 6 hours after sheath removal and up to 120 hours post PCI)	PPS
D	Concomitant medication		

Table 6.2: 1 (continued) Important protocol violations

Category/ Code	Description	Example/Comment	Excluded from

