6.6 HANDLING OF MISSING DATA AND OUTLIERS

A major goal of the trial is to obtain virtually complete follow-up of vital status and full collection of outcome event data. As mentioned in [Section 7.4](#), all patients lost to follow-up will be treated as censored at the time of last known vital status. This section contains details of how censoring will be performed for patients who do not experience outcome events.

The CTR will contain a summary of the number and percentage of patients with (and without) complete follow-up of vital status in each treatment group.

Due to the nature of the adjudication process, it may not be possible to classify bleeds under every bleed definition (i.e. TIMI and BARC). In these instances, the bleed classification will be left missing and no imputation will be attempted. Classification of bleeds under the ISTH definitions should not be left missing by the IAC.

In general, missing investigator INR ranges will be imputed with the standard guideline range for this patient population which is 2-3. The exception to this is for patients in Japan who are ≥ 70 years old. The guideline range for these patients is 2 – 2.6.

Missing or incomplete AE dates/times are imputed according to BI standards (see “Handling of missing and incomplete AE dates”) [[1](#)]. The same philosophy will be applied to missing or incomplete outcome event and concomitant medication dates/times. Incomplete dates of temporary study medication discontinuation and restart will be imputed. See the TSAP Analysis Dataset (ADS) Plan for further details. Other special handling for missing/incomplete dates/times will be documented in the RPM.

Other missing data will not be imputed. If date of birth/age is missing for a patient, they will not be included in models that use age group as a stratifying factor.

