7.4 PRIMARY ENDPOINT

This is a prospective, randomised, open label, blinded endpoint (PROBE), active comparator trial and the clinical endpoints are being adjudicated by an IAC in a blinded fashion. The IAC

Charter contains details of the outcome event adjudication criteria. The study will employ a time to first event analysis (using a stratified Cox proportional hazards regression model) and it is assumed that all patients will be observed until first primary endpoint event or until the last patient entered has completed at least six months of treatment (up to an anticipated maximum duration of approximately 30 months for the first patient entered). The trial will be monitored by an independent DMC.

This study is designed to test two safety hypotheses in NVAf patients that have undergone a successful PCI (elective or due to ACS) with stenting and were treatment naïve or were receiving oral anticoagulant treatment (either with warfarin, another VKA or other novel oral anticoagulant) before the procedure.

The primary endpoint, measured from date of randomisation to end of observation period, is:

- Time to first ISTH MBE or CRNMBE

as determined by the IAC. Only positively adjudicated events will be included in the analyses. They will be analysed using the stratified Cox proportional hazards regression model including age group (non-elderly or elderly [<70 or ≥ 70 years old in Japan and <80 or ≥ 80 years old everywhere else]) as a stratifying factor and treatment arm (110mg DE-DAT vs warfarin-TAT and 150mg DE-DAT and 110mg DE-DAT combined vs warfarin-TAT). For the 150mg DE-DAT versus warfarin-TAT comparison, an unstratified model will be applied comparing 150mg DE-DAT versus warfarin-TAT (excluding elderly EU/ROW patients in the warfarin-TAT group). In addition, an unstratified sensitivity analysis of the non-elderly patients only will be conducted.

Models will be fitted for each comparison separately (110mg DE-DAT vs warfarin-TAT and 150mg DE-DAT vs warfarin-TAT). The Breslow method [9] will be used to handle tied failure times.

The primary analysis will be performed under the intention-to-treat framework on the FAS. Patients who discontinue study medication will be followed until the end of the trial for vital status, ECGs, AEs, OEs (including completion of the bleeding questionnaire) and concomitant medications. All patients will be analysed according to the treatment arm to which they were randomised.

Survival time

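### SAP 6.6 drops randomised patients with missing age from the age-stratified Cox models, and the SAP does not say whether recorded age or the IRT stratum defines the 150mg comparator

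*SAP*

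**What the plan says.** **Analysis set.** Protocol 7.3.1 puts the primary analysis under intention-to-treat on the "full analysis set of patients (FAS) that includes all randomised patients (regardless of whether they have received treatment"). It adds that the 110mg comparison covers every age and region. SAP 6.3 likewise keeps all consenting randomised patients in the arm to which they were randomised.

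**Model.** For the primary endpoint SAP 7.4 states: "They will be analysed using the stratified Cox proportional hazards regression model including age group". This applies to 110mg versus warfarin and to the combined doses versus warfarin. The 150mg comparison uses an unstratified model, "excluding elderly EU/ROW patients in the warfarin-TAT group". Elderly means 70 or over in Japan and 80 or over elsewhere.

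**Missing age.** SAP 6.6 states: "Other missing data will not be imputed". It continues: "If date of birth/age is missing for a patient, they will not be included in models that use age group as a stratifying factor".

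**Randomisation.** Protocol 7.5 states: "Patients will be randomised in permuted blocks, dynamically stratified by age", and also by region. Elderly patients outside the USA are allocated only to 110mg or warfarin. Protocol 7.3.1 gives this as the reason for removing elderly EU/ROW patients from the warfarin arm of the 150mg comparison.

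**Mis-stratification.** SAP Table 6.2:1, code C2, lists "e.g. forced randomization, mis-stratification" as an important violation. It leads to exclusion from the per-protocol set only.

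**The concern.** A patient who was randomised and followed would leave the confirmatory 110mg and pooled-dose tests because one baseline field is blank. That is not the analysis set which the protocol and SAP declare. It is also unnecessary: the value the model needs is the stratum in which the patient was randomised, and the IRT had to hold one to make the allocation.

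The second matter concerns the 150mg test. Its exclusion applies to the warfarin arm alone. That is sound only if it removes exactly the patients who could not have been allocated 150mg. The IRT stratum identifies those patients; recorded age may not. The SAP does not say which is meant. A missing-date-of-birth rule would be needed only if age group were derived from recorded age, so recorded age is suggested but not stated. Step 2 of the hierarchy is the 150mg non-inferiority test and it gates Steps 3 to 6, so membership of that comparison should not be left open.

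**Working it through.** **1. Which tests the missing-age rule reaches.** Steps 1 and 4 (110mg, bleeding) and Steps 3 and 5 (combined doses, thrombotic composites) use the age-stratified model, so the rule applies. Steps 2 and 6 (150mg, bleeding) use the unstratified model, so it does not. For a warfarin EU/ROW patient with missing age, the SAP simply gives no classification in the 150mg comparison.

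**2. Whether the stratum exists for everyone.** Protocol 4.1.2 and 7.5 have the IRT stratify by age and region. Outside the USA the allocation ratio itself depends on the age group (1:1:1 or 1:1). The IRT cannot allocate without an age stratum.

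**3. The plan's own power figure.** Inputs from Protocol 7.2 and 7.6: 334 events per pair of arms, margin 1.38, one-sided alpha 0.025. Equal allocation and a true hazard ratio of 1 are assumed.

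Power = Φ(½·√d·ln 1.38 − 1.960) = Φ(½ × 18.276 × 0.3221 − 1.960) = Φ(0.983) = 83.7%, against 83.6% stated. The figure reproduces.

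**4. Cost of dropping patients with missing age.** Let m be the share missing. The documents give none, so a range is shown. Events become 334 × (1 − m). Patients lost are out of 2 × 834 = 1668.

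| m (assumed) | Patients lost | Events | Power |
|---|---|---|---|
| 0 | 0 | 334 | 83.7% |
| 0.1% | about 2 | 333.7 | 83.7% |
| 0.5% | about 8 | 332.3 | 83.5% |
| 1% | about 17 | 330.7 | 83.4% |
| 2% | about 33 | 327.3 | 83.0% |
| 5% | about 83 | 317.3 | 81.8% |

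Up to 2% missing, the loss is at most 83.7 − 83.0 = 0.7 points. This concerns the bleeding non-inferiority test in Step 1.

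**5. The 150mg comparison if recorded age were used.** An EU/ROW patient aged 80 or over who is entered as under 80 is randomised 1:1:1. Allocated 150mg, the patient stays in the comparison. Allocated warfarin, the patient is removed as elderly.

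Let f be the share of the 150mg arm who are such patients, and r their hazard relative to the non-elderly. Both are assumptions. With their warfarin counterparts gone, the hazard ratio is multiplied by about b = 1 − f + f·r. Power at a true hazard ratio of 1, holding 334 events, is Φ(½·√334·(ln 1.38 − ln b) − 1.960).

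| f | r | b | Power |
|---|---|---|---|
| 0 | any | 1.000 | 83.7% |
| 0.5% | 2 | 1.005 | 82.6% |
| 1% | 2 | 1.010 | 81.4% |
| 2% | 2 | 1.020 | 78.9% |
| 2% | 3 | 1.040 | 73.4% |

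If the exclusion is made by IRT stratum, mis-entered patients stay in both arms and b = 1.

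**The case against.** The strongest reply is that the missing-age rule may never be used. Age is needed for inclusion criterion 1, for IRT stratification and for the Cockcroft-Gault creatinine clearance behind exclusion criterion 12. This is a fair expectation. It makes the exclusion probably empty, but it does not reconcile the rule with the declared analysis set.

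On the 150mg comparison, a reader might infer that the SAP defines the comparator by recorded age and so builds in a one-sided exclusion. The documents do not support that. No available text names the data source; detailed derivations are deferred to the technical plan. SAP 4 changes the age grouping because the randomisation factor changed in Japan, and the protocol's reason for the exclusion rests on allocation. Both fit the IRT reading. Under that reading a warfarin-only exclusion is the correct concurrent-control restriction, because the removed stratum contains no 150mg patients. A reader might also suppose that Japanese patients aged 70–79 were randomised under an 80-year cut; the documents do not say whether any were.

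Three further points stand. Any distortion of the kind worked through above would push the hazard ratio against 150mg, so it does not favour a false claim of non-inferiority or superiority. The planned sensitivity analysis in non-elderly patients restricts both arms and partly covers the problem. Code C2 removes mis-stratified patients from the per-protocol set in every arm, although that analysis may be skipped if fewer than 10% of treated patients are excluded. None of these settles membership of the confirmatory 150mg test.

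**Conclusion.** The missing-age exclusion is explicit. It contradicts the intention-to-treat set for Steps 1, 3, 4 and 5, and it is avoidable. Separately, the source that defines elderly EU/ROW for the 150mg comparator is unspecified. A small bias against 150mg arises only if recorded age is used, disagrees with the IRT stratum for some patients, and older patients bleed more. It cannot be said from these documents that the 150mg comparison is biased.

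The size is probably very small: at most about 0.7 points of power for up to 2% missing age, and a hazard-ratio factor of about 1.01–1.02 if 1–2% of the 150mg arm were mis-stratified at twice the hazard. All these shares and hazards are assumed. This is a free improvement, not a design error.

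**What to change.** In SAP 6.6 and 7.4:

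- Define the age-group stratum by the IRT stratum at randomisation.
- Define membership of the 150mg comparison by the IRT age and region stratum, that is, patients who could have been allocated 150mg when randomised.
- Delete the exclusion for missing date of birth or age.
- Use recorded age only in a sensitivity analysis.

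The cost is a few sentences of SAP text. The documents do not state that the IRT stratum is already in the analysis database; if it is not, it must be transferred from the IRT. Planned events, sample size and power do not change.

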6.7 BASELINE, TIME WINDOWS AND CALCULATED VISITS

The baseline assessment is the last measurement made (or sample taken) prior to first study drug administration. The first study drug administration should occur at Visit 2. Any assessments made on this day, where time is not collected, are assumed to be prior to study drug administration. This does not apply to adverse events and outcome events where it will be assumed that events occurred on-treatment.

Concomitant medication is considered a baseline medication, if taken on the day of randomisation.

Actual dates will be used for assigning adverse events and outcome events to the appropriate treatment period as defined in [Section 6.1](#). Windowing will not be applied as the main objective of this trial is the collection of outcome events, which are not necessarily associated with clinic visits.

7. PLANNED ANALYSIS

Patient disposition (number of patients screened, randomised, treated, discontinued, etc...) will be presented for all patients.

The frequency of patients with IPVs will be presented. Those which lead to a patient being excluded from the PPS will be presented separately to those which do not.

Descriptive statistics for continuous variables will generally be n (number of patients with non-missing values), mean, standard deviation (SD), minimum, Q1 (lower quartile), median, Q3 (upper quartile), maximum. In general, means, medians, Q1 and Q3 will be presented to one more decimal place than the raw data and SDs will be presented to two more decimal places. Minima and maxima will be presented to the same number of decimal places as the raw data.

Tabulations of frequencies for categorical data will include all possible categories and will display the number of observations in a category as well as the percentage relative to the respective population. Percentages will be rounded to one decimal place. A missing category will be displayed if and only if there are actually missing values. Percentages will be based on all patients in the respective patient set whether they have non-missing values or not.

7.1 DEMOGRAPHIC AND OTHER BASELINE CHARACTERISTICS

Data from the demographic, medical history, PCI details and medication history eCRF pages will be presented descriptively by treatment group.

7.2 CONCOMITANT DISEASES AND MEDICATION

Only descriptive statistics are planned for this section of the report.

The frequency of patients with different concomitant diseases (baseline conditions) will be presented.

Medications will be classified using the World Health Organisation (WHO) dictionary (into e.g. antithrombotic therapies, bridging medications, P-gp inhibitors, P-gp inducers, etc...) and will be presented according to whether they were concomitantly taken during the on-treatment period (ignoring the REP) defined in [Section 6.1](#) or whether they are prior (i.e. those taken at baseline (=randomization visit)) or post therapy. Additional pooling of medication categories may also be necessary.

The usage of each concomitant medication of special interest during the treatment period (ignoring temporary interruptions) will be categorised according to the % of time that patients used that medication:

- Never used (0%)
- Used at least one time
- 0% < and ≤50% of the time

- 50% <and <100% of the time
- Always used (100%)

Only medications in the following categories will be presented:

- Antiplatelet medication
- Thrombolytic agents
- Novel direct oral anticoagulants
- Parenteral anticoagulants
- Vitamin K antagonists
- GPIIb/IIIa antagonists
- Therapies for bleeding management

Medications may be combined or removed from the table, if too few patients have taken them during the treatment period.

7.3 TREATMENT COMPLIANCE

Compliance will be summarised descriptively using the TS. The time period after permanent discontinuation from study medication and the time period during any temporary discontinuation of study medication will not be included in the calculation of the denominator.

Compliance to dabigatran etexilate

Based on capsule counts, treatment compliance (%) will be calculated as:

$$\frac{\text{Number of tablets actually taken} \times 100}{\text{Number of tablets which should have been taken}}$$

This value will be entered directly into the eCRF.

For patients who had a temporary discontinuation of dabigatran etexilate, the time interval between the day after temporary discontinuation and restart of medication should not be used in the calculation of the denominator.

A patient will be considered as non-compliant for a particular dosing interval if the number of doses taken is not between 80-120% of the expected number of doses.

Descriptive statistics will be presented for patients' overall compliance with dabigatran etexilate during the treatment period. This will be assessed using information from the trial medication compliance eCRF page. Mean compliance will be calculated per patient by weighting their reported % compliance according to how long it has been since their last clinic visit.

The mean compliance and the percentage of patients with compliance <50%, 50- <80%, 80 - <120%, ≥ 120% will be summarised by visit and overall.

Time in therapeutic range (TTR, warfarin)

The quality of warfarin therapy for each patient will be assessed by reporting the number of International Normalised Ratio (INR) values within the investigator indicated therapeutic target range at the time of the measurement, as well as those above and below these ranges. The following additional ranges will be investigated: 2.0 to 3.0, 2.0 to 2.5 and 2.5 to 3.0. The Rosendaal method will be used to evaluate the percentage of time that a patient's INR is in range (i.e. time in therapeutic range, TTR). This will be calculated for each patient, for each centre, for each country and for the whole study. The mean and median percentage of time in target INR range will be calculated for each centre and each country during the trial conduct to monitor the INR control. The percentage of time in target INR range for each country and for the trial will be reported.

For patients who had a temporary discontinuation of study warfarin, the time interval between the day after the temporary discontinuation and restart of medication will not be counted. If INR is evaluated during the first week after randomisation, those INR values will not be used in calculating TTR.

The Rosendaal method: assume the INR value between two measurements will vary linearly from the value of the first to the value of the second measurement, divide the time between two measurements in days, fit a linear equation using the two measured INR values, and then calculate the INR for each day in the interval. The percentage of time when INR is in target range is calculated for each patient. The intended target range for each patient is indicated by the investigator on the INR log page of the eCRF.

The frequency of the INR monitoring will be assessed using descriptive statistics.

Evaluation of INR measurements will include the following:

Mean and median percentage of time in target INR range over time

Frequency of patients with percentage of time in target INR range: < 45%, ≥45-<55%, ≥55-<65% and ≥65%

Frequency of patients with percentage of time in target INR range: <60%, ≥60-<75% and ≥75%

Medication interruptions:

The number of patients with temporary interruptions of study medications and the reasons for the interruptions will be summarised. In addition, the number of days with interruptions of study medications will be summarised descriptively. This will not include the addition of the REP (6 days). The number of patients with permanent interruptions of study medication are summarised in the patient disposition tables.

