4.3 TREATMENT COMPLIANCE

Patients are requested to bring all remaining trial medication including empty package material with them when attending visits.

Dabigatran Etexilate:

Based on capsule counts, treatment compliance will be calculated as the number of capsules taken, divided by the number of capsules which should have been taken according to the scheduled period, multiplied by 100.

Doses taken on the current visit day will be excluded from the count and doses taken on the previous visit day will be included in the count.

$$\text{Treatment compliance (\%)} = \frac{\text{Number of tablets actually taken} \times 100}{\text{Number of tablets which should have been taken}}^1$$

A patient will be considered as non-compliant if the number of doses taken is not between 80-120% of the expected number of doses. If compliance does not meet this range the patient should be asked to provide an explanation and re-informed about the purpose and conduct of the trial. Non-compliance should be discussed with BI.

General principles regarding the evaluability of non-compliant patients are outlined in [Section 7.3](#). Decisions about evaluability of patients will be made at the Blinded² Report Planning Meeting (BRPM) and at the latest prior to database lock.

Warfarin:

Warfarin compliance will be monitored by means of the INR rather than by pill counts as it is a more accurate and biologic measure of pharmacodynamic effect than pill counts. Investigators will be able to assign INR monitoring to a clinic outside the investigational site and dose adjustments will be made according to usual clinical practice. However, the Investigator will be responsible for reporting INR results, dose management of the patient and drug accountability of the warfarin prescribed. Patients must have the INR measured at least every two weeks for first three months, when commencing warfarin for the first time, otherwise at least monthly measurement are required. More frequent INR measurements may be done as necessary at the discretion of each Investigator or anticoagulation clinic. To aid Investigators, a validated nomogram, will be provided in the ISF, which will indicate recommended dose changes and INR re-testing times for different INR values. This nomogram requires more frequent INR monitoring after out-of-range INR values have occurred.

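### Warfarin patients who go months without an INR test can still count as compliant, because TTR is interpolated across any gap and violation C3 has no rule for missing INR

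*SAP*

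**What the plan says.** Protocol 4.3 monitors warfarin compliance through INR instead of pill counts. Patients starting warfarin for the first time are tested at least every two weeks for three months; "otherwise at least monthly measurement are required".

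SAP 7.3 converts INR values to TTR day by day. The instruction is to "assume the INR value between two measurements will vary linearly from the value of the first to the value of the second measurement". Two exclusions are specific to INR. First, "If INR is evaluated during the first week after randomisation, those INR values will not be used in calculating TTR". Second, for temporary interruptions, "the time interval between the day after the temporary discontinuation and restart of medication will not be counted". Time after permanent discontinuation is also left out. Nothing is said about long intervals between tests while the patient is on warfarin.

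SAP Table 6.2:1, item C3, defines warfarin non-compliance as "time in therapeutic target range for warfarin patients <45% (also on a visit-wise basis", and adds: "Patients will be flagged if they exhibit non-compliance for two consecutive visits or more". The consequence is exclusion from "PPS, but only from start of non-compliance onwards". No other item in the table concerns missed INR tests. On testing itself, SAP 7.3 says only: "The frequency of the INR monitoring will be assessed using descriptive statistics".

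SAP 6.6 does not impute other missing data, and no rule says how C3 classifies a visit whose TTR cannot be computed. Under SAP 6.3, a treated patient with no important violation is in the PPS.

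**The concern.** The protocol asks for INR at least monthly, but the analysis rule never checks that it was done. Absent testing has two possible outcomes: the straight line supplies values for the untested days, or there is no later INR and so no TTR. In the second case C3 cannot act, because a missing value is not below 45%. In the first, it acts only if the invented line happens to be out of range for long enough.

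The PPS is one of the robustness checks on a non-inferiority primary analysis, and it is meant to hold patients who followed the protocol. On dabigatran, adherence is judged by capsule counts against 80-120% limits. On warfarin, a patient can pass C3 with hardly any INR data. Reported TTR also includes untested days, and Protocol 4.3 sets TTR beside a 60% threshold and the 64% mean from the sponsor's earlier atrial fibrillation trial.

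**Working it through.** The documents give no figure to reproduce here, so the SAP rule was applied to example series. The INR values are assumptions. The range used is 2.0-3.0, whereas the SAP uses each investigator's indicated target. Clinic visits are about three-monthly in the first year (Protocol 6.2.2).

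**Common set-up.** INR is 2.4 at every test up to day 91, followed by a 182-day gap to day 273 (month 3 to month 9). The gap spans two visit intervals of 91 days each. Where testing resumes, INR is 2.5 on days 303, 334 and 365.

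**Formula.** Days in range before the line leaves the range = 182 × (distance from 2.4 to the limit) ÷ (total change).

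| INR on day 273 | Days in range in the gap | Month-6 TTR | Month-9 TTR | C3 flag |
|---|---|---|---|---|
| 2.6 | all 182 | 100% | 100% | no |
| 1.5 | 182 × 0.4/0.9 = 80.9, so 80 whole days | 80/91 = 88% | 0% | no |
| 1.0 | 182 × 0.4/1.4 = 52 | 52/91 = 57% | 0% | no |
| 4.5 | 182 × 0.6/2.1 = 52 | 52/91 = 57% | 0% | no |
| never retested | none evaluable | missing | missing | no |

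In rows two to four only one visit falls below 45%, so the two-visit condition is not met. In the last row overall TTR is 100%, from 91 − 14 = 77 evaluable days (first usable INR on day 14). A patient with one INR or none after week 1 has no TTR and is not flagged either.

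**Counter-example.** INR 1.5 just before the gap and 1.6 after it gives 0% and 0%, and C3 flags the patient.

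**Grid.** All pairs of end values from 1.0 to 5.0 in steps of 0.1 were tried, unweighted, so this is not a prevalence estimate. Of 1,681 pairs, 721 (43%) are flagged. Where the first value is in range, 92 of 451 (20%) are flagged.

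**Do gaps push TTR upward?** INR values were drawn independently from a log-normal distribution centred on the geometric middle of the range, √6. The spread was set so that the patient is truly in range 40% or 30% of the time. One six-month gap was compared with monthly testing over the same period.

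| True time in range | Mean TTR, gap | Mean TTR, monthly | Flagged at both visits, gap | Flagged at both visits, monthly |
|---|---|---|---|---|
| 40% | 0.49 | 0.49 | 28% | 22% |
| 30% | 0.37 | 0.37 | 40% | 46% |

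Mean TTR does not move, and the flag rate moves in opposite directions in the two rows.

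**Is a gap limit enough?** With a limit of 42, 56 or 90 days (assumed values), the 182 gap days drop out and evaluable days fall from 351 to 169. In the 2.4-to-1.0 series, in-range days are 77 + 52 + 73 = 202 without the limit and 77 + 73 = 150 with it. Overall TTR rises from 202/351 = 58% to 150/169 = 89%. The month-6 and month-9 values become missing, and C3 still does not flag the patient. A limit on interpolation therefore needs a rule for missing coverage alongside it.

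**The case against.** The main objection is that little depends on this. The primary analysis is on the full analysis set, and no step of the hierarchy uses TTR. The PPS is a sensitivity set for the primary endpoint, and its analysis may be dropped if fewer than 10% of treated patients are excluded (SAP 6.3). All of that stands, and it limits the point to a minor one.

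There are also other safeguards. Protocol 3.3.4.1 says treatment should be stopped for persistent non-compliance or failure to follow the protocol, and the on-treatment analysis then censors six days after the last intake. INR control is monitored by centre and country during the trial. Evaluability is reviewed before database lock, and the technical SAP and analysis dataset plan, which are not among the documents reviewed, could contain a gap rule. These may catch some patients, but none is a written criterion in the documents at hand, and in an open-label trial a fixed rule is preferable to case-by-case judgement.

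Three stronger readings are tempting and not supported:

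- **Gaps always score as in range and inflate reported TTR.** The score depends on the values at both ends. Out-of-range values at both ends are flagged, and mean TTR was the same with and without the gap in the simulation.
- **The PPS hazard ratio is biased towards non-inferiority.** That would need the share of untested patients and their relative bleeding rate. The documents give neither, and if untested patients had stopped warfarin the bias could run the other way.
- **Such patients have no compliance evidence at all.** The flow chart schedules drug accountability for warfarin patients from Visit 3, Protocol 4.3 makes the investigator responsible for it, and Protocol 4.1.6 has supplies checked at each visit. C3, however, uses none of this for warfarin.

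**Conclusion.** The gap in the rule is real. As the SAP is written, a warfarin patient who misses the required INR testing for months can score as in range, or have no TTR, and be kept in the PPS as compliant. This follows from three features read together: interpolation without a maximum interval, a C3 criterion that needs a computed value at two consecutive visits, and no violation for missed INR.

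Its size cannot be stated. The documents do not say how many patients would be affected, and neither the direction nor the amount of any shift in reported TTR or in the PPS hazard ratio can be derived. The examples show what the rule permits, not how often it happens. The consequence is confined to the reported TTR and the PPS robustness analysis. The conclusion assumes that the technical documents not supplied contain no gap or coverage rule.

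**What to change.** In SAP 7.3, set a maximum interval for interpolation and leave longer on-warfarin gaps out of both the numerator and the denominator of TTR. About eight weeks, twice the monthly minimum, would be reasonable; the documents supply no value, so the choice is the sponsor's.

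In C3, count a warfarin visit interval as non-compliant if it contains no INR, or if most of its on-drug days are not covered by evaluable INR. Apply this under the existing two-consecutive-visit rule. Keep the present exemptions for documented interruptions.

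Report the number of warfarin patients affected, and how many leave the PPS as a result.

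The cost is a few lines of SAP text and a small change to the TTR program. Protocol 4.1.4 already has all available INR values entered in the eCRF, so no new data are needed. Some warfarin patients will leave the PPS, and reported TTR may move in either direction.
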